**Patient demographics:**

In total, 24 patients were recruited in this study. Follow-up moments were between August 2022 and March 2023. Inclusion and surgery took place between July 2023 and January of 2023. A total of 15 participants completed the primary study outcomes measures (on scar quality and patient-reported outcomes) and were included for analysis. The patient demographics are presented in Table 1. The median age of the participants was 29.8 years (range 25–34.5) in the standard dressing group and 34.6 in the PICO-7 group (range 27–42). The average prior cesarean sections were 1.4 (range 1–3) in the standard dressing group and 1.7 (range 1–3) in the PICO-7 group. Only one of the patients declared to have experienced any problematic scarring previous to surgery (e.g., hypertrophy and/or keloid). Most of the included patients were Caucasian (87.5%).

Table 1: Descriptive Statistics

Variable	Standard dressing (N = 5)	PICO (N = 10)
Age, Mean (SD)	29.8 (4.7)	34.6 (7.5)
BMI, Mean (SD)	37.2 (11.9)	34.0 (5.1)
Number of Prior C-sections, Mean (SD)	1.4 (0.9)	1.7 (1.1)

Language		
English	4 (100%)	5 (50%)
Spanish	0	5 (50%)
Missing	1	
Ethnicity		
Non-Hispanic or Latino	5 (100%)	6 (60%)
Hispanic or Latino	0	4 (40%)
Race		
Black/African American	4 (80%)	5 (50%)
White	1 (20%)	1 (10%)
Unknown/not reported	0	4 (40%)

The Patient Scar Assessment Scale (POSAS) rates 6 variables: scar-related pain, itching, color, stiffness, thickness, and irregularity. Each parameter is scored on a 1- to 10-point ordinal scale, with 1 indicating that the scar is comparable with normal skin and 10 reflecting the worst imaginable scar, as seen in Figure 4 and Figure 5. The sum of the 6 individual parameters ranges from 6 (normal skin) to 60 (worst scar).

At week 2, the average patient score was 33 in the standard dressing group versus 19 in the PICO-7 group. At week 4, the average patient score was 24.5 in the standard dressing group versus 25 in the PICO-7 group. At week 6, the average patient score was 26.5 in the standard dressing group versus 13.0 in the PICO-7 group. The observer score was measured between 4-6 weeks at the patients postpartum visit. The average observer score was 19 in the standard dressing group versus the 16 in the PICO-7 group.

Table 2: Comparison of patient POSOS scores between the groups

Variable	Standard dressing	PICO
POSAS score Week 2, Median (Q1-Q2)	33.0 (17-49) [N = 2]	19.0 (16-32) [N = 5]
POSAS score Week 4, Median (Q1-Q2)	24.5 (15-34) [N = 2]	25.0 (6-27) [N = 5]
POSAS score Week 6, Median (Q1-Q2)	26.5 (16-36.5) [N = 4]	13.0 (10-16.5) [N = 8]

Table 3: Comparison of observer POSOS scores between the groups

Variable	Standard dressing	PICO
Observer score, Median (Q1-Q2)	19.0 (11.5-39) [N = 4]	16 [N = 1]
Overall opinion of scar, Median (Q1-Q2)	7.0 (4-10) [N = 2]	2 [N = 1]

### Secondary Outcomes

Table 3: Incisional Healing Complications

Variable	Standard dressing (N = 5)	PICO (N = 10)
Post-operative complications		
None	4 (80%) Where is the other person in the n	8 (80%)
Rash around incision due to adhesives	0	1 (10%)
Neuropathic pain	0	1 (10%)
Infection (superficial or deep)	0	0
Dehiscence	0	0

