# Cosmetic Outcome of PICO-7 Dressing Compared to Standard Abdominal Dressing for Repeat Cesarean Section

## ABSTRACT

**Background and Objectives:** This study was designed to compare cosmetic results in patients who have undergone repeat cesarean section through a Pfannenstiel skin incision when using a PICO-7 negative pressure wound dressing versus standard abdominal dressing postoperatively.

**Methods:** Twenty four English and Spanish speaking patients who underwent repeat Cesarean Section via Pfannenstiel skin incision from July 28, 2022 to January 4, 2023 at Eskenazi Hospital in Indianapolis, Indiana were enrolled. Patients were evaluated using the Patient and Observer Scar Assessment (POSAS) Scale at two, four and six weeks postoperatively. Healthcare providers were asked to fill out the Patient and Observer Scar Assessment Scale at the patients postpartum visit, which was between four to six weeks postoperatively.

**Results:** The median patient assessment scale and observer assessment scale (general) values were higher in the PICO group than in the standard abdominal dressing group at 2 weeks, equivalent at 4 weeks and lower at 6 weeks. There were no differences in the number of postoperative wound infections or readmissions, and there was 1 reported rash due to the adhesives in the PICO group that required it to be removed early.

**Conclusion:** Due to low recruitment and low response rate, this study as it currently stands cannot evaluate the PICO-7 dressing versus standard abdominal dressing. Because of the potential physical and psychological benefit of reducing complicated scar formation, further studies could be performed with a higher recruitment and follow up that would be able to provide information to determine if the PICO-7 versus other NPWT could be beneficial at improving patient's scar satisfaction after a repeat cesarean section.

Key Words: *Cesarean, POSAS, PICO, NPWT, cosmetic*

**Disclosure:** A portion of this study was supported financially by Smith and Nephew, the manufacturers of the PICO-7 NPWT device.

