### **Data Collection:**

The Patient Scar Assessment Scale (POSAS) rates 6 variables: scar-related pain, itching, color, stiffness, thickness, and irregularity. Each parameter is scored on a 1- to 10-point ordinal scale, with 1 indicating that the scar is comparable with normal skin and 10 reflecting the worst imaginable scar. The sum of the 6 individual parameters ranges from 6 (normal skin) to 60 (worst scar).

The POSAS patient survey was e-mailed to participants at the two, four, and six-week time intervals and data collected and stored via REDCap. Participants were sent each survey up to 3 times until a response was logged. If they did not respond electronically, each patient was then called up to 3 times. The POSAS observer survey was completed and collected at the time of the patient interview (routinely a postpartum visit). The observer (MD/DO/NP seeing the patient) was also asked to upload a picture of the cesarean section scar into the EMR. Baseline patient characteristics including maternal age, BMI, and number of prior cesarean sections were abstracted from the EMR.

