### **Study outcomes:**

The primary study outcome was to compare aesthetic appearance and patient satisfaction at 6 weeks postoperative of a repeat C-section in NPWT-PICO dressing vs. standard abdominal dressing. The primary time point of interest was at 6 weeks as we expected the most improvement to be seen at that later time point.

The secondary objective was to compare incision healing complications up to 42 days postoperatively between the standard dressing group vs. the PICO NPWT group.

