### Discussion/Conclusions:

In this study, we assessed the influence of incisional negative pressure wound therapy on scar development and patient satisfaction with their cosmetic outcome. We performed a pilot randomized controlled trial to test two equivalent incisions. Generally, the results of this study showed a potential small difference in favor of iNPWT in patient-reported outcome measures with a lower score on the POSAS score at 6 weeks and a lower observer score and overall score of the scar at 4-6 weeks postpartum. These outcomes could not be analyzed for any sort of statistically significant values due to the low recruitment and even lower patient follow up and response rate despite attempting to reach patients by both several emails and phone calls.

Strengths of this study include an even 1:1 block randomization at a single site (Eskenazi Hospital) with a robust Labor and Delivery unit with a diverse patient population. Limitations of this study include a small sample size and low patient follow up response rate, which yielded data that was unable to be analyzed for statistical significance. In statistical considerations in study design, we expected a 20% drop-out by 6 weeks. However in our study, we had a 35% drop out rate (no response in any of the three surveys), and only 12.5% of patients filled out all 3 weeks of the surveys. 42% of patients did not attend their scheduled postpartum visit at the 4-6 week mark. Many of the other

studies that were performed using NPWT compared to standard abdominal dressing were done to evaluate the benefits on wound healing and preventing surgical site infections. The study that was performed to evaluate potential patient cosmesis benefits when using NPWT compared to standard dressing was a gender affirming mastectomy, which was ultimately an elective and cosmetic surgery which could have contributed to having higher patient follow up rates. It is possible that patient follow up and participation could have been lower than expected as a cesarean section is a medically necessary and not a cosmetic surgery, and the participants of this study were all recruited at a county hospital that serves a largely low income and resource population. Lastly, the participants of this study were all taking care of newborn children as well. All of these can cause difficulty with follow up and are also potential barriers to care, as seen by the overall low follow up for medical care at the post partum visit.

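### The complication table for the secondary objective places only 4 of 5 standard-dressing women, covers 15 of the 24 enrolled, and gives no count behind the abstract's readmission statement

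*Protocol*

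**What the plan says.** The secondary objective (Protocol, Study outcomes) is to "compare incision healing complications up to 42 days postoperatively between the standard dressing group vs. the PICO NPWT group". It is not limited to women who answered the scar survey.

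The result is in the table titled Incisional Healing Complications (Protocol, Secondary Outcomes; the second of two tables numbered 3). Its headers are N = 5 for standard dressing and N = 10 for PICO. The first standard-dressing cell reads "4 (80%) Where is the other person in the n", and every listed complication in that column is 0. The table states no population, time window or method of ascertainment.

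On who was analysed, Patient demographics says: "A total of 15 participants completed the primary study outcomes measures (on scar quality and patient-reported outcomes) and were included for analysis". Statistical Analysis gives 24 enrolled.

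The abstract reports: "There were no differences in the number of postoperative wound infections or readmissions". It also concludes that "this study as it currently stands cannot evaluate the PICO-7 dressing versus standard abdominal dressing".

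**The concern.** Three things do not fit together.

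- **The count.** The standard-dressing column falls one woman short of its own header, and the text left in the cell asks about exactly that shortfall. It is neither a redaction nor a PDF-reading fault. The same cell supplies one side of the table's equal 80% figures.
- **The coverage.** A complication outcome to day 42, by dressing group, is shown for 15 of 24 enrolled women, and nothing on the table says it is limited.
- **The abstract.** It reports a between-arm result on readmissions for which the table has no row.

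What is at stake is the accuracy of a reported secondary outcome. A reader or a later evidence synthesis would take counts from this table, and in a column of five one record moves the rate by 20 points.

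**Working it through.** **1. Row sums against headers** (Secondary Outcomes table; rows in order: none, rash, neuropathic pain, infection, dehiscence)

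- Standard dressing: 4 + 0 + 0 + 0 + 0 = 4, header N = 5. One woman is unplaced.
- PICO: 8 + 1 + 1 + 0 + 0 = 10, header N = 10. This agrees.

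The printed percentages reproduce on the header Ns: 4/5 = 80% and 8/10 = 80%. A woman with more than one complication could only push the row sum above N, so double counting does not explain a sum below N.

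**2. What the fifth woman's status does to the comparison**

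Complication-free, standard minus PICO. The difference has a Newcombe 95% interval, and p is two-sided Fisher. PICO is 8/10 throughout (exact 95% CI 44.4 to 97.5%).

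| Fifth woman | Standard (exact 95% CI) | Difference, points | p |
|---|---|---|---|
| Had an unlisted complication, or a listed one with a printed zero in error | 4/5 = 80% (28.4 to 99.5) | 0 (-44.8 to 35.0) | 1.00 |
| Status unknown, kept in the denominator | 4/5 = 80% (28.4 to 99.5) | 0 (-44.8 to 35.0) | 1.00 |
| Had no complication | 5/5 = 100% (47.8 to 100) | +20 (-25.8 to 51.0) | 0.52 |
| Status unknown, excluded | 4/4 = 100% (39.8 to 100) | +20 (-31.0 to 51.0) | 1.00 |

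The point comparison moves between 0 and +20 points, and every interval includes zero.

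**3. Whether the documents rank these readings**

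They do not. Table 1 handles missing values in two ways. For Language, the standard-dressing column drops one missing woman, so 4 of the 5 is printed as 100%. For Race, the PICO column keeps 4 women of unknown or unreported race in the denominator of 10 and prints them as 40%. The printed 80% is therefore compatible with a woman of unknown status as well as with one who had a complication.

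**4. Coverage**

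- In the table: 5 + 10 = 15, the same Ns as Table 1 and the 15 women included for analysis.
- Not in the table: 24 - 15 = 9, and 9/24 = 37.5%.
- Placed in a row: 4 + 10 = 14, and 14/24 = 58.3%.

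The Discussion reports that "we had a 35% drop out rate (no response in any of the three surveys". Of 24, 35% is 0.35 x 24 = 8.4. That lies between 8/24 = 33.3% and 9/24 = 37.5% and does not settle whether the 9 absent women are the survey non-responders. What defines the 15 is itself unclear: Statistical Analysis gives 15 responders at week 6, while Table 2 shows 4 + 8 = 12 scores at that week.

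**5. The abstract's sentence**

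- Infection: the table prints 0 v 0, so the statement matches the row. The rows place only 14 women, so infection status is not verified for the fifteenth.
- Readmission: no row in the table, and no mention elsewhere in the readable Protocol or SAP.

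**The case against.** The strongest reply is that nothing rests on this table. The authors state that the study cannot evaluate the dressings, the readable text draws no conclusion from 80% v 80%, and tests on 5 and 10 women decide nothing. That stands, and it limits the point to a minor correction. It does not make the column add up or supply a readmission count.

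A second reply is that the limitation is visible: the text says 15 women were analysed, and the complication table carries the same headers as Table 1. This stands in part. A careful reader can see that the table covers 15 women, but not why a day-42 complication outcome should be confined to them or how complications were found. Figure 3 (enrollment and follow-up) is not shown and may account for the other 9.

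A reader might also infer more than the documents support:

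- *That equal rates require a complication of an unlisted type.* They could also arise from a wrong zero in a listed row, or from a woman of unknown status kept in the denominator. In a column already shown to be mis-tallied, the zeros cannot be taken as verified.
- *That missing status is the less likely explanation.* This would rest on Table 1's Language row alone, and the Race row points the other way.
- *That the infection result is confirmed for all 15 women.* The rows place 14.
- *That the table was restricted to survey responders and is biased as a result.* The restriction is inferred from matching Ns. Selection on follow-up is possible, but it is not demonstrated, and its direction and size cannot be computed from the text.

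**Conclusion.** The point holds as a reporting error in a secondary outcome. One of five standard-dressing women is unplaced, and the drafters' own query confirms that the gap was noticed and not closed. The printed equality of 80% v 80% is unverified: the difference is 0 or +20 points depending on one record, with no change in inference. Complication status is missing from the readable text for 9 of 24 enrolled women (37.5%), against an objective that is not restricted to the analysed 15. The readmission half of the abstract's sentence is unsupported in the readable text; the infection half matches the printed row but rests on 14 placed women.

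This takes the PICO column and the header Ns as printed, and allows that the figures not shown may explain the 9 absent women. The primary outcome and the conclusion that the study cannot evaluate the dressings are unaffected. Severity is minor.

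**What to change.** 1. Resolve the fifth standard-dressing woman from her record, or show her in a row for unknown status. Correct the count and percentage, state the denominator rule, and delete the query.
2. Label the table as covering the 15 analysed women, state its window and method of ascertainment, and show 9 as not reported. If outcome data exist for the others and abstracting them is permitted, report all 24 by assigned arm with an unknown row instead.
3. Limit the abstract's infection statement to the women with known status.
4. Support the readmission phrase with counts by arm, or delete it. Deletion is enough, because readmission is not named in the secondary objective.

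The minimum costs one record query, one relabelled table and an edit to one abstract sentence, with no new patients or visits. The 24-record option depends on things the documents do not establish. The only record abstraction that Data Collection describes is for baseline: "Baseline patient characteristics including maternal age, BMI, and number of prior cesarean sections were abstracted from the EMR". The downside is that some day-42 statuses will stay unknown, since "42% of patients did not attend their scheduled postpartum visit at the 4-6 week mark" (0.42 x 24 = 10.1, about 10 women).

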### Discussion/Conclusions:

In this study, we assessed the influence of incisional negative pressure wound therapy on scar development and patient satisfaction with their cosmetic outcome. We performed a pilot randomized controlled trial to test two equivalent incisions. Generally, the results of this study showed a potential small difference in favor of iNPWT in patient-reported outcome measures with a lower score on the POSAS score at 6 weeks and a lower observer score and overall score of the scar at 4-6 weeks postpartum. These outcomes could not be analyzed for any sort of statistically significant values due to the low recruitment and even lower patient follow up and response rate despite attempting to reach patients by both several emails and phone calls.

Strengths of this study include an even 1:1 block randomization at a single site (Eskenazi Hospital) with a robust Labor and Delivery unit with a diverse patient population. Limitations of this study include a small sample size and low patient follow up response rate, which yielded data that was unable to be analyzed for statistical significance. In statistical considerations in study design, we expected a 20% drop-out by 6 weeks. However in our study, we had a 35% drop out rate (no response in any of the three surveys), and only 12.5% of patients filled out all 3 weeks of the surveys. 42% of patients did not attend their scheduled postpartum visit at the 4-6 week mark. Many of the other

studies that were performed using NPWT compared to standard abdominal dressing were done to evaluate the benefits on wound healing and preventing surgical site infections. The study that was performed to evaluate potential patient cosmesis benefits when using NPWT compared to standard dressing was a gender affirming mastectomy, which was ultimately an elective and cosmetic surgery which could have contributed to having higher patient follow up rates. It is possible that patient follow up and participation could have been lower than expected as a cesarean section is a medically necessary and not a cosmetic surgery, and the participants of this study were all recruited at a county hospital that serves a largely low income and resource population. Lastly, the participants of this study were all taking care of newborn children as well. All of these can cause difficulty with follow up and are also potential barriers to care, as seen by the overall low follow up for medical care at the post partum visit.

Due to the open-label nature of the study, neither the participant nor the observer were blinded to the intervention. The impact of attribution bias or placebo effect is difficult to assess in an open-label study. Additionally, the questionnaire used consisted of multiple sub-questions that equated to an overall score, which has the potential to result in false significant outcomes based on multiple testing and the non-linear conversion table from absolute value to the 0–100 scale. Lastly, only one patient questionnaire (POSAS) was used in this study.

Moving forward, to be able to attempt to achieve a recruitment value to be able to analyze for statistical analysis, it would be prudent to attempt to include a larger population of patients. At Eskenazi Hospital in particular, two languages were not inclusive enough for adequate recruitment in this study in the short amount of time that recruitment was open. It would be extremely beneficial for recruitment to be able to include languages such as Haitian Creole in addition to Spanish and English. In the literature, other clinical studies on iNPWT on scar outcomes present a variety of scar outcome measures such as the Vancouver Scar Scale (VSS), Stony Brook Scar Evaluation Scale (SBSES), Visual Assessment Scale (VAS), Manchester Scar Scale (MSS) and the BIS (Body Image Scale) were used. It could be useful to incorporate more scales to ensure that there was not a false interpretation of scar outcomes by using only one scale.

In conclusion, this pilot randomized controlled trial was unable to provide any statistically significant data, but did show a lower overall score in the PICO-7 group vs the standard abdominal dressing group at the 6 week mark for both patients themselves and for observers. Because of the potential physical and psychological benefit of reducing complicated scar formation, further studies should be performed with a higher recruitment and follow up percentage that would be able to provide information to determine if the PICO-7 or other NPWT could be beneficial at improving patient's scar satisfaction after a repeat cesarean section.

Qualitative scar assessment

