## **Methods:**

### **Study design and participants:**

This study was a single site, randomized controlled trial at a teaching hospital in Indiana for patients undergoing a repeat cesarean delivery. Participants were randomized using 1:1 block randomization to placement of a PICO-7 dressing or a standard abdominal dressing (generally telfa, ABD gauze dressing, tegaderm +/- steristrips) at the time of cesarean. The standard abdominal dressing was removed approximately on postoperative day (POD) 1-2 and the PICO-7 dressing was removed approximately on POD 3-4 (prior to discharge) or at POD7 in the office. If the patient with a PICO dressing remained inpatient for longer than 7 postoperative days, the PICO dressing was removed prior to POD7, in accordance with device instructions. The patients were given routine postoperative incision care instructions during their inpatient stay, which includes education per OB-GYN residents, attending staff, and nursing.

Participants in both groups were sent electronic POSAS surveys at the two, four and six week postop window with primary outcome being aesthetic appearance (cosmesis) at six weeks. Observers (healthcare providers) were asked to complete a POSAS survey at the postpartum visit (~4-6 weeks postoperative) to rate scar quality. Participants were offered compensation with a \$25 Amazon gift card for participants who completed the requested follow up in the study. These were provided by Smith and Nephew.

The eligibility criteria is listed here as follows:

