### **Statistical Analysis:**

Characteristics of the study population were summarized using descriptive statistics. 24 patients were recruited and enrolled in the study. Out of these 24, only 3 patients that responded to all three (2-, 4- and 6- week) POSAS surveys. 15 patients responded to the 6 week assessment survey, which was the primary outcome of this study. For this reason, statistical analysis that would provide a statistically significant value was unable to be performed.

[figure not shown]

Figure 3: Enrollment and follow up

Results:

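### The report points towards PICO from responders only (4 vs 8 scores at week 6), without saying that response may differ by arm or how far the result depends on the missing women

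*Protocol*

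**What the plan says.** Protocol, Study design and participants: "Participants were randomized using 1:1 block randomization to placement of a PICO-7 dressing or a standard abdominal dressing". The Discussion lists this as a strength: "Strengths of this study include an even 1:1 block randomization at a single site".

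Protocol, Statistical Analysis: "24 patients were recruited and enrolled in the study". Patient demographics: "A total of 15 participants completed the primary study outcomes measures (on scar quality and patient-reported outcomes) and were included for analysis". Table 1 divides those 15 into 5 standard and 10 PICO. Table 2 has patient scores from 2 vs 5 women at week 2, 2 vs 5 at week 4, and 4 vs 8 at week 6. The observer table has 4 vs 1 total scores and 2 vs 1 overall opinions.

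From these responders the Discussion reports "a potential small difference in favor of iNPWT in patient-reported outcome measures". Its closing paragraph says the trial "did show a lower overall score in the PICO-7 group vs the standard abdominal dressing group at the 6 week mark", and applies this to observers as well as patients. The limitations name small size, low overall response and the open-label design. They do not mention response by arm.

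**The concern.** Randomisation protects a comparison when outcomes are known for the women randomised, or when missingness is unrelated to arm and outcome. Here PICO supplies at least twice as many patient scores at every survey, while observer scores run the other way. Neither participants nor observers were blinded, so willingness to respond could depend on the dressing received. If it did, the apparent advantage could reflect who answered rather than the dressing.

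The analysed groups also look different: mean age is 29.8 vs 34.6, and Spanish speakers are 0 of the 4 with known language vs 5 of 10. Table 1 covers only the 15 analysed women, so a reader cannot tell whether these differences arose at randomisation or through non-response.

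The caveat the report does give, that significance could not be assessed, concerns precision. Selective response is a matter of bias, and more precision would not cure it.

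**Working it through.** **The plan's yardstick.** SAP and Protocol, Statistical Considerations: 0.7 x 7.2 = 5.04, so the stated 5 points reproduces. The week-6 medians are 26.5 (standard) and 13.0 (PICO), a gap of 13.5 points. 13.5 / 5 = 2.7, so a gap called small is 2.7 times the difference the plan was built to detect.

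**Response by arm.** Arm sizes are not in the readable text. I assume 12/12 and vary it.

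| Standard/PICO randomised | Any survey | Fisher p | Week 6 | Fisher p |
|---|---|---|---|---|
| 11/13 | 45% vs 77% | 0.21 | 36% vs 62% | 0.41 |
| 12/12 | 42% vs 83% | 0.09 | 33% vs 67% | 0.22 |
| 13/11 | 38% vs 91% | 0.01 | 31% vs 73% | 0.10 |

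Observer scores at 12/12 are 4/12 vs 1/12, p = 0.32. Equal any-survey response would need arms of 8 and 16 (5/8 = 10/16 = 62.5%), which is not an even allocation.

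**Dependence on the missing women (12/12).** Week-6 scores are missing for 12 - 4 = 8 standard and 12 - 8 = 4 PICO women.

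*Medians, all missing women given 13.* In the standard arm at most 4 of 12 values lie below 13 and at most 4 above, so the 6th and 7th values are both 13. In the PICO arm the observed median is already 13, and adding four 13s keeps it there. The gap is 13 - 13 = 0. The same holds at 11/13 and 13/11.

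*Approximate means* (reported medians standing in for means, since no means are given), all missing women given 13:
- Standard: (4 x 26.5 + 8 x 13) / 12 = 17.5
- PICO: (8 x 13 + 4 x 13) / 12 = 13.0
- Gap: 4.5 points

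*Any common score c:* gap on means = [(106 + 8c) - (104 + 4c)] / 12 = (2 + 4c) / 12. This is 2.2 at c = 6, 4.5 at c = 13 and 9.0 at c = 26.5. It is positive over the whole 6-60 scale.

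*Different scores by arm:* with x for missing standard and y for missing PICO women, the gap on means is zero when 106 + 8x = 104 + 4y, that is y = 2x + 0.5. For example, x = 13 needs y = 26.5. Missing PICO women must therefore score worse than missing standard women.

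*Extremes on means:*
- x = 6, y = 60: 12.8 - 28.7 = -15.8
- x = 60, y = 6: 48.8 - 10.7 = +38.2

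**Precision.** I read the bracketed ranges in Table 2 as lower and upper quartiles, take SD = IQR/1.349, and use medians for means.
- Standard: (36.5 - 16) / 1.349 = 15.2
- PICO: (16.5 - 10) / 1.349 = 4.8
- SE = sqrt(15.2²/4 + 4.8²/8) = 7.79 (unrounded SDs); Welch df = 3.3
- 95% interval: about -10 to +37 points

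**Counts that disagree.** Statistical Analysis says 15 women answered the week-6 survey, but Table 2 has 4 + 8 = 12. The Discussion's 35% with no survey at all is close to (24 - 15)/24 = 37.5%, so 15 may be the any-survey count. If 5 and 10 did answer at week 6, the least favourable fill on means still reverses the order: (5 x 26.5 + 7 x 6)/12 = 14.5 vs (10 x 13 + 2 x 60)/12 = 20.8.

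**The case against.** The strongest reply is that the report does not oversell. Its abstract concludes that the study as it stands cannot evaluate the dressing. The Discussion calls the difference potential, says no significance could be assessed, and concedes small numbers, poor response and open-label bias. Table 2 already prints N by arm and week. This stands: the report does not claim that PICO works. It does, however, state a direction twice, and none of these caveats covers arm-related response.

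A reader might infer that 5 vs 10 contradicts the 1:1 claim or shows faulty randomisation. It does not. The claim describes allocation, the split describes responders, and the allocation statement can remain.

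A reader might also infer that response is shown to depend on arm. The evidence is weaker than that. The denominators are assumed, the week-6 p-value at 12/12 is 0.22, and the only p below 0.05 in the table needs 13/11 and the any-survey count.

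Finally, the zero gap on medians owes much to 8 of 12 standard-arm values being set to one constant. On means the same fill leaves 4.5 points, close to the plan's 5. That objection is right as far as it goes, and it is why both figures are given.

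**Conclusion.** The concern holds as a reporting and sensitivity problem. The two directional statements rest on 12 of 24 women at week 6, split 4 to 8, with no interval and no account of the other half. Depending on what is assumed about the missing women, the 13.5-point gap can vanish or reverse, shrink to about 4.5 points, or persist at about 9. An approximate interval of -10 to +37 includes no difference.

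These figures do not show that the gap is false. They are bounds, and on means non-responders with the same average in both arms shrink the gap without removing it. The conclusion rests on assumed 12/12 arms, medians used for means, SDs from quartiles, and the Table 2 counts.

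Two wording faults add to it. The gap is called small although it exceeds the plan's own target. The closing paragraph places the observer result at six weeks, although it is a single PICO form from a visit scheduled at 4-6 weeks.

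**What to change.** 1. Keep the 1:1 allocation statement. Add as a limitation the analysed split by arm, with randomised denominators at each week and for observer forms.
2. Reconcile the 15 week-6 responders in Statistical Analysis with the 12 in Table 2.
3. Give the week-6 difference with an unequal-variance interval and a short tipping-point table that varies missing scores in both arms.
4. Replace the Discussion's phrase about a potential small difference with: *observed median difference of 13.5 points, too imprecise and too exposed to missing data to favour either dressing*.
5. Correct the closing paragraph so that the observer result reads 4-6 weeks, N = 4 vs 1.

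The cost is a few hours of analysis on existing data and a less favourable conclusion. No new data are needed.
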